14.4 TREATMENT OF AES

The Investigator will ensure that all subjects who experience an adverse event are treated per Standard of Care until the event is resolved or no further clinical improvement is expected, or (if applicable) the subject is LTFU.

14.5 CLINICAL EVENTS COMMITTEE (CEC)

An independent Clinical Events Committee (CEC) comprising of three physicians who are familiar with the study indication will review and adjudicate ***all adverse events and protocol deviations*** to remove Investigator-based bias in AE/PD classification and allow for the poolability of data. The CEC will consist of physician(s) who are not affiliated with the Sponsor and are not participating in the study. The recommendations of the CEC override the Investigator's classification and become part of the clinical trial data set.

Clinical Study Protocol

The CEC will adjudicate all AEs and potentially reclassify the severity, seriousness, anticipatedness, and relationship to the device/procedure. The CEC will also adjudicate all PDs and potentially reclassify the deviations in terms of whether they are minor or major deviations.

15. SOURCE DOCUMENTATION

The Investigator will be supplied with one physical binder per subject. The binder will contain paper Case Report Forms(CRFs) for collection of study data. It is expected that these CRFs will be the source of all study data. It is possible that additional supplemental source may be captured once the study is underway, but the primary source of all study data is expected to be the paper CRFs.

16. STUDY MONITORING

16.1 SITE MONITORING

The study will be monitored to ensure that it is conducted in conformance with the monitoring plan by an independent CRO to assess continued compliance with the protocol, recognized Good Clinical Practices, FDA's IDE guidance documents, and federal regulations outlined in 21 CFR 812.43(d) and 21 CFR 812.46. In addition, monitoring verifies that study records are adequately maintained, that data are reported in a satisfactory manner with respect to timeliness, adequacy, and accuracy, and that the Investigator continues to have sufficient staff and facilities to conduct the study safely and effectively.

The study may also be subject to a quality assurance audit by the Sponsor or its designees, as well as inspection by appropriate regulatory authorities. It is important that the Investigator and relevant study personnel are available during on-site monitoring visits or audits and that sufficient time is devoted to the process.

The organization responsible for monitoring the study is:

MCRA, LLC
[name]

In addition to ensuring adequate communication between the Investigators and the Sponsor, the CRO's duties may include on-site visits and review of study documents and reported data per the Clinical Monitoring Plan. The CRO study representatives will be provided with appropriate device and protocol training prior to the study and will follow a Monitoring Plan for all study-related monitoring activities.

16.2 MONITORING ACTIVITIES

On-site monitoring visits may include, but are not limited to a pre-study Site Initiation Visit, periodic Interim Monitoring Visits, and a Close-Out Visit at the end of the site's participation in the study.

The Investigator will allocate adequate time for monitoring activities. The Investigator will also ensure that the monitor or other compliance or quality assurance reviewer is given access to the study-related documents and study-related facilities and has adequate space to conduct the monitoring visit.

Monitoring visits will be documented on monitoring visit reports. On-site and remote monitoring will aim to verify that:

- Compliance with the clinical protocol and applicable regulations is being maintained

- Source data is verified and signed-off upon as accurate
- Subject files are accurate and complete
- Subject withdrawal has been documented (if applicable)
- Subject non-compliance has been documented (if applicable)
- The Investigator and site staff are informed and knowledgeable of all relevant document updates concerning the clinical investigation
- Only authorized individuals are performing study-related functions
- The investigational device is being used according to the protocol and instructions for use
- Adequacy of staffing and facilities
- Signed and dated ICFs have been obtained from each subject
- CRFs and queries are complete
- All adverse events are reported to the Sponsor
- All serious and unanticipated adverse device events are reported to the Sponsor and the IRB
- All other required IRB reports, notifications, applications, submissions, and correspondence are maintained in the Investigator's files and are accurate
- Corrective and preventive actions have been implemented (if applicable)

16.3 FREQUENCY OF VISITS

To ensure that the study is conducted in accordance with the terms of the clinical protocol, study monitors may visit each investigational site throughout the duration of the study per the Clinical Monitoring Plan. The exact frequency of visits shall be determined shall depend upon factors such as but not limited to the following:

- Rate of subject enrollment
- Experience of the Investigator in conducting clinical studies
- Record of previous site compliance

17. AUDITS AND INSPECTIONS

Participation as an Investigator in this study implies acceptance of potential inspection by government regulatory authorities. The Investigator must also be prepared to permit study-related audits and inspections by the Sponsor, CRO, IRB and the site's institutional compliance and quality assurance groups. The Investigator will ensure the capability for inspections of applicable study-related facilities, records and reports.

18. STATISTICAL ANALYSIS PLAN

18.1 STUDY HYPOTHESIS

The primary hypothesis is that the probability of experiencing device-related Serious Adverse Events (SAE) for subjects treated with the investigational device is smaller than the performance goal of 1%. Formally, that hypothesis to be tested are:

H_0 : The expected proportion of subjects with device-related SAE up to Day 30 (p_T) is greater than or equal to the performance goal (PG) of 1.0%.

H_A : The expected proportion of subjects with device-related SAE up to Day 30 (p_T) is less than the performance goal (PG) of 1.0%.

These hypotheses may be symbolically represented as:

$$H_0: p_T \geq PG = 1.0\%$$

$$H_A: p_T < PG = 1.0\%$$

Where p_T is the device-related SAE rate for subjects treated with the investigational device.

If the Bayesian Posterior Probability that $p_T < PG$ is greater than or equal to .975, the alternative hypothesis will be accepted, and it will be concluded that the device meets the performance goal.

18.2 SAMPLE SIZE ANALYSIS

A review was performed on all the published and unpublished clinical data on the OsteoProbe device. In order to systematically review and identify potential data sources for the informative prior initial criteria was established. In order for the data to be included as an informative prior the following criteria needed to be met:

1. a minimum of 30 days follow-up on patients;
2. the OsteoProbe procedure was administered in a manner consistent with the IDE;
3. the data commented on safety around serious adverse events.

First, a total of 40 published articles were reviewed. Of the published literature, and four published studies met criteria "1" (Patient Follow-up) and "2" (OsteoProbe Procedure) outlined in Section 2, above. The following are the four literature articles:

- (1) Sundh D, et al. [JBMR. 2018;33(7):1242-1251],
- (2) Pérez-Sáez MJ et al. [Bone. 2018;116:290-294],
- (3) Robert Guerri-Fernandez, et al [AIDS 2018, 32:913–920], and
- (4) Mellibovsky L, et al. [JBMR 2015;30(9):1651-1656].

However, two (Sundh et al and Pérez-Sáez et al) of the four did not explicitly state the safety outcomes in the study. Given the articles did not explicitly state the safety result, the two articles were excluded from the informative prior. Only two studies met all three criteria, Robert Guerri-Fernandez et al and Mellibovsky L et al.

Table 6. Literature Data Evaluation

Study	Criterion 1: >30 day follow up	Criterion 2: Procedure with OsteoProbe	Criterion 3: Language explicitly	Informative Prior Inclusion
-------	--------------------------------	--	----------------------------------	-----------------------------

			stating safety results	
Sundh D, et al	X	X		No
Pérez-Sáez MJ et al	X	X		No
Robert Guerri-Fernandez, et al	X	X	X	Yes
Mellibovsky L, et al	X	X	X	Yes

Additionally, a review was performed on all unpublished and ongoing studies with the OsteoProbe device. The same criteria were applied in evaluation of these potential datasets. A total one unpublished or two ongoing studies were found meet the three criteria for inclusion as an informative prior. The table below summarizes the evaluation and inclusion of this information. Each of the included clinical data is further summarized below.

Table 7. Unpublished or Ongoing Clinical Data Evaluation

Study	Criterion 1: >30 day follow up	Criterion 2: Procedure with OsteoProbe	Criterion 3: Language explicitly stating safety results	Informative Prior Inclusion
OHSU (unpublished)	X	X	X	Yes
LUMC (ongoing)	X	X	X	Yes
BARWON (ongoing)	X	X	X	Yes

The summary findings are shown below Table 8.

Table 8: Informative Prior Data

Study	# Subjects	Device Related SAEs
Robert Guerri-Fernandez (2018)	40	0
Mellibovsky L, et al (2015)	52	0
OHSU	18	0
LUMC (ongoing)	110*	0*
BARWON (ongoing)	50*	0*
Total	270*	0*

*Anticipated at the time of De Novo submission

These five studies contain or will contain 270 subjects with an anticipated rate of zero subjects experiencing a device-related Serious adverse events. Given there is no variability between these studies, the data are pooled together and collectively constitute the informative prior. To be conservative, the initial assumption will only consider 215 subjects with zero device-related adverse events. The informative prior was constructed as Jeffries prior plus the data in Table 8, that is, Beta(.5 + data, .5 + data).

When there are zero device-related SAEs in 40 prospective subjects, the posterior probability will be .9765 and the device will have been shown to meet the performance goal. Therefore, only if there are zero device-related SAE's will the alternative hypothesis be accepted.

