	
A literature review was performed by the Sponsor who identified six studies with clinically relevant data to serve as an informative prior. These six studies contain 215 subjects with zero subjects experiencing device-related serious adverse events. Given there is no variability between these studies, the data are pooled together and collectively constitute the informative prior. The informative prior was constructed as Jeffries prior plus the data from the literature, that is, Beta(.5 + data, .5 + data).
 
When there are zero device-related SAEs in 40 prospective subjects, the posterior probability will be .9765 and the device will have been shown to meet the performance goal. Therefore, only if there are zero device-related SAE's will the alternative hypothesis be accepted.

Statistical Plan
	
The primary hypothesis is that the probability of experiencing device-related Serious Adverse Events (SAE) for subjects treated with the investigational device is smaller than the performance goal of 1%. Formally, the hypothesis to be tested is:
 
H_0: The expected proportion of subjects with device-related SAE up to Day 30 (p_T) is greater than or equal to the performance goal (PG) of 1.0%.
 
H_A: The expected proportion of subjects with device-related SAE up to Day 30 (p_T) is less than the performance goal (PG) of 1.0%.
 
These hypotheses may be symbolically represented as:
 $H_0: p_T \geq PG = 1.0\%$ $H_A: p_T < PG = 1.0\%$ 
Where p_T is the device-related SAE rate for subjects treated with the investigational device.
 
If the Bayesian Posterior Probability that $p_T < PG$ is greater than or equal to .975, the alternative hypothesis will be accepted, and it will be concluded that the device meets the performance goal.

STUDY MANAGEMENT	

Principal Investigator
	
[name] MD Meridian Clinical Research, LLC, [name]

Clinical Research Organization (CRO)
	
MCRA, LLC [name]

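### Section 18.2 defines the prior for the only hypothesis test by Table 8 (270 subjects, .9875 after 0/40), but its stated .9765 holds only for an unitemised 215-subject prior

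*Combined protocol and SAP*

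**What the plan says.** The primary safety hypothesis is the only formal test. Under Section 18.1 the device meets the 1% performance goal if the posterior probability of a device-related SAE rate below 1% is at least .975.

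Section 18.2 describes the prior in four steps:
- Table 8 lists five studies with 40, 52, 18, 110 and 50 subjects and no device-related SAEs. The text says "These five studies contain or will contain 270 subjects". The rows of 110 and 50, and the total, carry the footnote "Anticipated at the time of De Novo submission".
- The pooled data are then said to form the informative prior.
- The next sentence reads "To be conservative, the initial assumption will only consider 215 subjects with zero device-related adverse events".
- The sentence after that reads "The informative prior was constructed as Jeffries prior plus the data in Table 8".

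The section then concludes: "When there are zero device-related SAEs in 40 prospective subjects, the posterior probability will be .9765", and says that the goal has thereby been met.

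Section 1 gives the same 215 and the same .9765 but another origin: "These six studies contain 215 subjects with zero subjects experiencing device-related serious adverse events", and "The informative prior was constructed as Jeffries prior plus the data from the literature". In Section 18.2, of the published articles, "Only two studies met all three criteria". Those two contribute 40 + 52 = 92 subjects. The other three sources are one unpublished and two ongoing studies.

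Section 18.4 says only that historical data will be updated with trial data. It gives no count, list of studies or cut-off.

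**The concern.** The prior that Section 18.2 defines and the posterior that it reports do not belong together. A statistician programming the primary analysis would have to choose between 215, 270 and whatever the ongoing studies have reached by then. Calling 215 an initial assumption suggests that a later value will replace it, but nothing says what that value is or when it is fixed.

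The choice carries weight because history supplies most of the evidence: 215/255 = 84% of the subjects in the posterior, or 270/310 = 87%. In an open-label, single-arm study, a prior that is not locked could also be enlarged after the results are known. Section 18.9 requires only that changes to the analysis plan be documented in the study report.

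**Working it through.** **Inputs.** Performance goal .01 and threshold .975 (18.1, 18.4); Jeffreys start Beta(.5, .5) plus historical data (18.2); H = 215 or 270 historical subjects with no events (18.2, Table 8); 40 trial subjects (18.2).

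**Formula.** With e events among n subjects in total (historical plus trial), the posterior is Beta(.5 + e, .5 + n − e). The quantity needed is its distribution function at .01.

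**The plan's own figure.** H = 215 and 0/40 give n = 255, hence Beta(.5, 255.5) and P = 0.97649. This reproduces .9765. Neighbouring totals do not: n = 254 gives 0.97622 and n = 256 gives 0.97676. Only H = 215 yields .9765.

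**The prior as defined by Table 8.** 40 + 52 + 18 + 110 + 50 = 270. With 0/40, n = 310, hence Beta(.5, 310.5) and P = 0.98748, or .9875.

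**Can 215 be traced?** No combination of whole Table 8 studies sums to 215. The nearest are 52 + 110 + 50 = 212 and 40 + 18 + 110 + 50 = 218.

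**The two priors compared, no historical events:**

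| Situation | H = 215 | H = 270 |
|---|---|---|
| Prior alone | .9625 | .9802 |
| After 0/40 | .9765 | .9875 |
| After 1/40 | .837 | .899 |

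With complete data, both priors pass 0/40 and fail 1/40.

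**Incomplete data.** Section 18.5 imputes missing subjects from the posterior of the observed data only. That can be read in more than one way.
- *Trial-only Jeffreys posterior, one subject missing, 39 event-free.* The imputation posterior is Beta(.5, 39.5), so the chance of imputing an event is .5/40 = .0125. Averaging over the imputed outcome:
  - H = 215: .9875 × .97649 + .0125 × .83683 = .9747, which fails.
  - H = 270: .9875 × .98748 + .0125 × .89889 = .9864, which passes.
- *Subjects simply absent from the analysis set, no imputation.* With H = 215, 35 event-free subjects give n = 250 and .9751 (pass), and 34 give n = 249 and .9748 (fail). With H = 270, 34 give n = 304 and .9866 (pass).

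**One historical device-related SAE and 0/40.** This is one event in 255 or 310 subjects, so P = .837 or .899. Both fail.

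**The case against.** The strongest reply is that 215 is a deliberately cautious planning value and 270 the count expected by submission. On that view nothing is miscalculated. The sentence giving 215 stands directly before the one that refers to Table 8, and Sections 1 and 18.2 agree on 215 subjects, no events and .9765. Much of this stands: a reader might infer an arithmetic error, and there is none. The 215 may be accrual to date in the ongoing studies. But the reply does not say which prior enters the final analysis, and the definition in 18.2 still points to Table 8.

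It can also be said that the choice does not matter, since the planned decision rule is the same under both priors. That is right for 40 complete subjects and no historical events, and a reader should not infer that the choice reverses the planned result.

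On missing data, a reader might infer that the 215 prior always needs at least 35 event-free subjects. The plan does not support that as a general rule, because Section 18.5 imputes missing subjects and does not simply drop them. The threshold of 35 applies only where subjects are absent and not imputed.

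Finally, the plan does not hide its zero-event assumption. Table 8 shows zero, the 215 sentence says zero, and the Beta form would admit historical events. What it lacks is a cut-off and a statement of what one such event would do to the claim about 0/40.

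**Conclusion.** The concern holds as an inconsistency in how the prior is specified, and it should be corrected before the primary analysis. The stated prior (270 subjects) gives .9875, and the stated posterior (.9765) belongs to 215 subjects whose make-up and cut-off are not given. Sections 1 and 18.2 disagree on the number and kind of sources: six studies from the literature against five, of which two are published.

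The consequences are limited but real:
- With 270 subjects the criterion is met before anyone is enrolled (.9802). With 215 it is not (.9625).
- With one missing subject and trial-only imputation, the decision differs (.9747 against .9864). This rests on one reading of Section 18.5.
- The unconditional statement that 0/40 meets the goal depends on no device-related SAE in any included study. One such event gives .837 or .899, which fails under either prior.

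A reader might go further and infer that only the 110 subjects in unmarked rows (40 + 52 + 18) are really available. The documents do not support that: Section 1 speaks of 215 subjects in the present tense, and nothing says that the ongoing studies would be left out.

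**What to change.** State one prior in identical terms in Sections 1, 18.2 and 18.4: number of subjects, number of device-related SAEs, contributing studies and data cut-off. Lock it before trial results are known, and count any device-related SAE in the included studies up to the cut-off.

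- **If 215 is kept:** replace the reference to Table 8 with the per-study counts that make up 215, correct the six studies and the attribution to the literature in Section 1, and make any 270-subject analysis supportive.
- **If 270 is used:** restate .9765 as .9875 and disclose that the prior alone already exceeds .975.
- **In either case:** say that 0/40 meets the goal only if the locked prior contains no device-related SAE.

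The cost is some wording and one set of per-study counts, with no extra subjects and no change to procedures. The downside for the sponsor is that the conclusion is shown plainly to rest mainly on historical data.

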18.3 STUDY POPULATIONS

18.3.1 Primary Analysis Set

All subjects with a time of procedure start recorded will be included in the Primary Analysis Set. The Primary Analysis Set will be utilized in testing of the primary safety endpoint.

18.3.2 Per Protocol Analysis Set

A per protocol (PP) analysis may be performed excluding enrolled subjects that are subsequently found to not meet the inclusion or exclusion criteria based objective criteria or that experience an intercurrent event during follow-up that makes the device-related SAE endpoint uninterpretable.

18.3.3 Training Cases

There are no training cases for this protocol.

18.4 TESTING OF PRIMARY SAFETY HYPOTHESES

The primary safety hypothesis will be tested by determining the Bayesian posterior probability that the device-related SAE rate is less (i.e., better) than the performance goal. The Bayesian posterior probability will be calculated by updating historical data with prospective trial data. The Bayesian posterior probability will be calculated through numerical integration with regards to the performance goal of .01. When the Bayesian posterior probability of the conditional device-related SAE rate is higher than .975, the alternative hypothesis will be accepted, and it will be concluded that the device has met the specified performance goal of 1%. As stated above, this will only occur when there are zero out of 40 events.

Supporting analyses will summarize the Bayesian posterior probabilities that the device-related SAE rate is lower than varying reference margins.

95% credible intervals of the device-related SAE rate will also be reported without using an informative prior distribution.

18.5 MISSING DATA/SENSITIVITY ANALYSIS

Given the short follow-up, there is not expected to be a large amount of missing data. Detailed descriptions of the reason(s) for missingness will be provided for every missing subject and timepoint. Subjects missing data will be multiply imputed using the posterior distribution of the observed data only. Bayesian posterior summarizes will characterize best- and worst-case scenarios as sensitivity to MAR assumption necessary for the imputation model. There will be no imputation for secondary effectiveness endpoints.

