10. EARLY DISCONTINUATION SUBJECTS

10.1 LOST TO FOLLOW-UP (LTFU)

Subjects who miss the final, 30-day study follow-up will be regarded as Lost to Follow-Up. Site staff should perform and document a minimum of three attempts to contact them via phone, and one attempt to reach them via certified mail to bring them in for the final study visit prior to considering the subject LTFU. The staff should document the date and type of attempted communication.

All efforts should be made to have subjects complete all follow-up visits but only subjects that miss the 30-day follow-up will be considered LTFU.

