10.4 USE OF DATA FROM EARLY DISCONTINUATION CASES

Study data collected previously for subjects who withdraw from the study, are discontinued from the study by the Investigator or LTFU will be included in the data analysis and clinical study report.

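### Section 18.5 can be read to impute missing outcomes from trial data alone while Section 18.4 analyses historical plus trial data; near 215 historical subjects this can turn a zero-event pass into a fail, and a closed-form posterior avoids the mismatch

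*Combined protocol and SAP*

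**What the plan says.** Section 18.4 defines the primary analysis: "The Bayesian posterior probability will be calculated by updating historical data with prospective trial data". The prior in Section 18.2 is Jeffreys plus the historical data. Success requires a posterior probability of at least .975 (Section 18.1) that the rate of device-related serious adverse events (SAEs) is below 1%. Section 18.4 adds: "As stated above, this will only occur when there are zero out of 40 events".

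On the historical total, Section 18.2 anticipates 270 subjects with no events but plans on fewer: "To be conservative, the initial assumption will only consider 215 subjects with zero device-related adverse events".

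On missing data, Section 18.5 says: "Subjects missing data will be multiply imputed using the posterior distribution of the observed data only". It also promises posterior summaries for "best- and worst-case scenarios as sensitivity to MAR assumption necessary for the imputation model". It gives no base prior, number of imputations or combining rule. It expects little missing data and states no rate.

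Three other sections bear on who is counted. Section 18.3.1: "All subjects with a time of procedure start recorded will be included in the Primary Analysis Set". Section 10.1: "only subjects that miss the 30-day follow-up will be considered LTFU". Section 10.4, on what enters the analysis: "Study data collected previously for subjects who withdraw from the study, are discontinued from the study by the Investigator or LTFU will be included".

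**The concern.** The phrase in Section 18.5 matches neither term of Section 18.4. The word 'only' may exclude the historical data, or it may exclude just the missing values. Two programmers could follow the plan faithfully and build different imputation models.

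On the trial-only reading, a missing subject is imputed as an event far more often than the analysis model implies, and the completed data are then analysed under a prior that disagrees with the imputations. At 215 historical subjects the planned pass clears .975 by only about .0015, so this can decide a trial with no observed events. Section 10.2 does not replace subjects withdrawn after treatment, so a lost outcome stays lost. The choice could also be made after the outcomes are known, because the study is open-label.

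**Working it through.** **Inputs.** Goal .01 and threshold .975 (Sections 18.1, 18.4); prior Beta(.5, .5 + n0) with zero historical events, n0 = 215 for planning and 270 anticipated (Section 18.2); 40 trial subjects (Section 7.2). Zero observed events throughout. Assumed, because the documents give no value: m missing outcomes among 40; a Jeffreys base for trial-only imputation; posterior probabilities averaged over a large number of imputations.

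**The plan's own figure.** With 0/40 events the posterior is Beta(.5, 255.5), and P(p < .01) = .97649. This is the plan's .9765. One event in 40 gives .83683, so the zero-event requirement also reproduces.

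**Trial-only imputation, one missing.** The 39 observed subjects give Beta(.5, 39.5). The imputed event probability is .5/40 = 1.25%. Averaging:

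.9875 × .97649 + .0125 × .83683 = .97475, a fail by .00025.

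**Historical data included, one missing.** Beta(.5, 254.5) gives .5/255 = 0.20%. Averaging:

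.99804 × .97649 + .00196 × .83683 = .97622.

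The closed-form posterior from the 39 observed, Beta(.5, 254.5), gives P(p < .01) = .97622 directly. The two agree for every m: averaging a posterior probability over draws from its own predictive distribution returns the posterior given the observed data.

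**Larger m at n0 = 215.** The number of imputed events is beta-binomial, from Beta(.5, .5 + 40 − m) for trial-only and Beta(.5, .5 + 215 + 40 − m) with historical data.

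| Missing | Trial-only, averaged | Section 18.4 model (closed form) |
|---|---|---|
| 1 | .97475 fail | .97622 pass |
| 2 | .97286 fail | .97594 pass |
| 3 | .97083 fail | .97566 pass |
| 4 | .96864 fail | .97538 pass |
| 5 | .96627 fail | .97509 pass |
| 6 | .96371 fail | .97480 fail |

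**Dependence on the historical total.** At 216, trial-only imputation passes with one missing (.97503) and fails with two (.97316). At 270 it passes with eight (.97509) and first fails with nine (.97280). The smallest historical total that passes trial-only is 216, 223, 230, 237 and 245 for one to five missing. Under the Section 18.4 model it is 211, 212, 213, 214 and 215.

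**Dependence on the base prior.** A uniform base is stricter: .97309 at 215 with one missing, and failure at 270 from five missing (.97420).

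**Simulation noise with historical data included, n0 = 215.** With 1,000 imputations about 19% of seeds fall below .975 at four missing and 42% at five, where the margins are .0004 and .0001. With 100,000 imputations these become 0% and 2%.

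**Bounds and tipping point.** For one missing at 215 the best and worst cases are .97649 and .83683. The event probability at which the averaged result reaches .975 is (.97649 − .975) / (.97649 − .83683) = .00149/.13966 = 1.07%. For two missing it is 0.53%. At 270 the values are 14.1% and 6.8%.

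**The case against.** **The effect is narrow.** The one-missing failure is by .00025 and disappears at 216. Section 18.2 calls 215 an initial, conservative assumption. At 270, nine of 40 outcomes would have to be missing, and Section 10.1 requires repeated contact attempts before a subject is declared lost. This largely stands. But 160 of the 270 (110 + 50) come from two ongoing studies and are marked as anticipated, so the final total is open.

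**Averaging is an assumption.** With one missing, 98.75% of trial-only completed data sets have no event and give .97649; a median over imputations would pass. This stands: the reversal depends on the combining rule, which the plan does not name. Averaging is the natural rule for a posterior probability.

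**The bounds already show the fragility.** They do, but they are sensitivity summaries. With one missing at 215 they fall on both sides of .975 and cannot set the primary result.

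**The closed form is the lenient reading.** True, and it must be disclosed. The argument for it is coherence: under the missing-at-random assumption that Section 18.5 itself makes, it is the exact result of the Section 18.4 model.

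**Stronger readings to avoid.** A reader might infer that Section 18.5 inflates false success. It does not: trial-only imputation makes success harder. A reader might infer that the plan has definitely chosen trial-only imputation; the wording does not settle that. A reader might turn the closed form into a rule of zero events and at least 250 subjects in total. At 270 historical subjects that rule is met with no prospective outcome at all (Beta(.5, 270.5) gives .98023), which the 40-subject wording in Section 18.4 does not permit.

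**Conclusion.** The point holds as a should-fix. Section 18.5 either imputes from a model that disagrees with Section 18.4 or adds simulation noise to a result available exactly. At 215 historical subjects with zero observed events, the choice reverses the conclusion for one to five missing outcomes, given a Jeffreys base and averaging. The error is in the conservative direction, is largest near 215, and at 270 needs nine missing.

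The documents leave two related matters unstated: whether an event-free subject who misses Day 30 counts as missing, and how a final visit on Day 20, inside the ±10-day window, relates to an endpoint that runs to Day 30. These need clarification only. A reader might infer that event-free early leavers should be dropped from the primary result while early leavers with events are kept. Sections 10.4 and 18.3.1 do not support that, because they retain these subjects' data and the full Primary Analysis Set.

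**What to change.** Replace the imputation sentence in Section 18.5 with:

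> The primary posterior is computed in closed form as Beta(.5 + x0 + x, .5 + n0 − x0 + `n_obs` − x), using the Section 18.4 prior. Here n0 and x0 are the historical subjects and events, `n_obs` is the number of Primary Analysis Set subjects whose primary outcome is known, and x is the number of these with a device-related SAE. Unknown outcomes are assumed missing at random.

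If imputation is kept, draw from that same Section 18.4 posterior and average the posterior probability over enough imputations to make simulation error negligible.

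Keep the .975 criterion together with zero prospective events and the planned 40 treated subjects. Keep the best- and worst-case bounds and add the tipping-point analysis. Add one sentence saying when an outcome is known, consistent with Sections 10.4 and 18.3.1.

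The cost is one paragraph and less programming, with no extra data. The downside to state is that at 215 a zero-event trial can pass with up to five unknown outcomes, against none under averaged trial-only imputation. At a true rate of exactly 1%, the chance of zero events is .99^40 = .669 with 40 known outcomes and .99^35 = .703 with 35.
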